Appendix 5: ADVERSE EVENTS OF SPECIAL INTEREST

An Adverse event of special interest (AESI) is a serious or non-serious adverse events of scientific and medical concern for which ongoing monitoring and rapid communication by the Investigator to the Sponsor is indicated. The following adverse events (AEs) for potential immune-mediated medical conditions as well as events associated with thrombosis and thrombocytopenia are AEs of special interest (AESIs) and include new onset of chronic illness (NOCIs). These events should be monitored for actively and reported to the Sponsor in an expedited manner as outlined in [Section 9](#).

Table 11: Adverse Events of Special Interest

Gastrointestinal disorders:	Liver disorders:
• Celiac disease	• Autoimmune cholangitis
• Crohn's disease	• Autoimmune Hepatitis
• Ulcerative colitis	• Primary biliary cirrhosis
• Ulcerative proctitis	• Primary sclerosing cholangitis
Metabolic diseases:	
• Addison's disease	• Diabetes mellitus type 1
• Autoimmune thyroiditis (including Hashimoto thyroiditis)	• Grave's or Basedow's disease
Coagulopathy:	
• Acquired amegakaryocytic thrombocytopenia	• Amegakaryocytic thrombocytopenia
• Axillary vein thrombosis	• Cavernous sinus thrombosis
• Cerebral venous thrombosis	• Deep vein thrombosis
• Disseminated intravascular coagulation	• Embolism venous
• Hepatic vein thrombosis	• Immune thrombocytopenia
• Intracranial venous sinus thrombosis	• Mesenteric vein thrombosis
• Portal vein thrombosis	• Pulmonary embolism
• Pulmonary thrombosis	• Pulmonary venous thrombosis
• Severe fever with thrombocytopenia syndrome	• Subclavian vein thrombosis
• Thrombocytopenia	• Thrombocytopenia purpura
• Thrombotic thrombocytopenia purpura	• Thrombosis
• Transverse sinus thrombosis	• Vena cava embolism
• Vena cava thrombosis	• Venous thrombosis
Musculoskeletal disorders:	
• Antisynthetase syndrome	• Polymyalgia rheumatic
• Dermatomyositis	• Polymyositis
• Juvenile chronic arthritis (including Still's disease)	• Psoriatic arthropathy
• Mixed connective tissue disorder	• Relapsing polychondritis
• Scleroderma, including diffuse systemic form and CREST Syndrome	• Rheumatoid arthritis

• Systemic lupus erythematosus	• Systemic sclerosis
• Spondyloarthritis, including ankylosing spondylitis, reactive arthritis (Reiter's Syndrome) and undifferentiated spondyloarthritis.	
Neuroinflammatory disorders:	
• Acute disseminated encephalomyelitis, including site specific variants (e.g., non-infections encephalitis, encephalomyelitis, myelitis, myeloradiculomyelitis)	
• Immune related peripheral neuropathies and plexopathies, including chronic inflammatory demyelinating polyneuropathy, multifocal motor neuropathy and polyneuropathies associated with monoclonal gammopathy	
• Cranial nerve disorders, including paralysis/paresis (e.g., Bell's palsy)	• Guillain-Barre syndrome, including Miller Fisher syndrome and other variants
• Multiple sclerosis	• Narcolepsy
• Optic neuritis	• Transverse Myelitis
• Myasthenia gravis, including Eaton-Lambert syndrome	
Skin disorders:	
• Autoimmune bullous skin diseases (including pemphigus, pemphigoid and dermatitis herpetiformis)	• Rosacea
• Alopecia areata	• Cutaneous lupus erythematosus
• Erythema nodosum	• Psoriasis
• Morphoea	• Sweet's syndrome
• Lichen planus	• Vitiligo
Vasculitis:	
• Large vessels vasculitis including: giant cell arteritis such as Takayasu's arteritis and temporal arteritis	
• Medium sized/and or small vessels vasculitis including: polyarthritis nodosa, Kawasaki's disease, microscopic polyangiitis, Wegener's granulomatosis, Churg-Strauss syndrome (allergic granulomatous angitis), Buerger's disease thromboangitis obliterans), necrotizing vasculitis and anti-neutrophil cytoplasmic antibody (ANCA) positive vasculitis (type unspecified), Henoch-Schonlein purpura, Behcet's syndrome, leukocytoclastic vasculitis	
Others:	
• Autoimmune glomerulonephritis (including IgA nephropathy, glomerulonephritis rapidly progressive, membranous glomerulonephritis, membranoproliferative glomerulonephritis, and mesangioproliferative glomerulonephritis)	
• Antiphospholipid syndrome	• Pernicious anemia
• Autoimmune hemolytic anemia	• Raynaud's phenomenon
• Autoimmune myocarditis/cardiomyopathy	• Sarcoidosis
• Autoimmune thrombocytopenia	• Sjogren's syndrome
• Goodpasture syndrome	• Stevens-Johnson Syndrome
• Idiopathic pulmonary fibrosis	• Uveitis

APPENDIX 6: SUMMARY OF CHANGES TO PROTOCOL**PROTOCOL VXA-NVV-108 HISTORY**

Name of the Document with Version Number	Date	Summary of Changes and Rationale
VERSION 1.0	17 FEB 2023	INITIAL VERSION
V ERSION 2.0	25 JUL 2023	

VXA-NVV-108 Protocol Amendment 1, Version 2.0 <DATE>

Protocol Amendment 1 (Version 2.0) of this phase 1 Norovirus GI.1/G2.4 bivalent protocol (VXA-NVV-108) was finalized on 17 Feb 2023, approved by the regulatory authority, South African Health Products Regulatory Authority, on 19 May 2023 and by the independent ethics committees which also serve as central ethics committees, Pharma Ethics Independent Research Ethics Committee on 14 June 2023 and the University of the Witwatersrand's Human Research Ethics Committee on 27 June 2023. It is being amended to clarify visit procedures, update language on contraception, update language on immunogenicity assessment, administrative updates throughout the protocol and correct other minor typographical errors. A description of the changes along with a brief rationale for each change is presented in the table below.

Section No. & Title	Description of Change	Brief Rationale
footer	Updated all footers-page numbers	Correct typos and pagination errors
Cover Page and headers and Signature Page	Updated Protocol Version and Date	Correct Protocol Version and date
Protocol Version History	Original Text: 12 Oct 2022 Page 78 Updated Text: 17 Feb 2023 Page 78	Updated typographical error
Table of Contents	Updated Table of Contents	Added Appendix 6 -Summary of Changes to the Protocol
Protocol Synopsis	Current Text: TBD CRO Updated Text:	Administrative detail updated

Protocol Synopsis- Eligibility Criteria and	Updated Exclusion Criteria #8	Clarification to collect infant medical record at screening and Day 1 and to provide infant vaccination record at Day 60 or later
Section 5.1 inclusion Criteria	
Original Text:
 
The nursing infant is the product of a singleton pregnancy AND does not have any of the following
 
Updated Text:
 
The nursing infant is the product of a singleton pregnancy AND does not have any of the following (therefore, subjects must be willing to provide the infant's medical record at screening and Day 1 and the infant's updated vaccine record at Day 60 or later):
	
Protocol Synopsis- Eligibility Criteria and	Updated Exclusion Criteria #21	Clarifications to the use of medications known to affect immune function
Section 5.1 Inclusion Criteria	
Original Text:
 
Use of medications known to affect the immune function (including but not limited to systemic corticosteroids, leukotriene modifiers, and JAK inhibitors) within 2 weeks before study drug administration or planned use during the active study period.
 
Updated text:
 
Use of medications known to affect the immune function (including but not limited to systemic corticosteroids, leukotriene modifiers, and JAK inhibitors) within 2 weeks before study drug administration or planned use during the active study period. Ophthalmic, inhaled, and intranasal steroids should follow these restrictions.
	
1.1 Schedule of Trial Activities Table 1.0 Schedule of Activities	
Added following text to Notes:
 
* Also collect the infant's medical record at screening and day 1 and the infant's updated vaccine record at D60 or later
	

	
Removed the following procedure from the SOA grid:
 
Remove breast milk from D15, Month 4
	

Section 3.2.1 Primary Endpoints
 
Immunogenicity
	
Breastmilk VPI specific (GI.1 and GII.4) IgA through the active period measured by Meso Scale Discovery (MSD) assay by dose level
 
Removed Day 15 from GMC and removed Day 1 to Day 15 GMFR
	

Section 3.2.2 Secondary Endpoints
 
Immunogenicity
	
Breastmilk VPI specific (GI.1 and GII.4) IgA through 6 months after study drug dose measured by Meso Scale Discovery (MSD) by dose level
 
Removed Day 120 from GMC and removed Day 1 to Day 120 GMFR
	

Section 7.1.1. Procedure to be followed on Screening Period (Day -45 to Day -1)
	
Current Text
 
The subject can use a manual breast pump if she does not wish to manually express her breastmilk.
 
Timepoints for breastmilk and infant stool sample collection must be thoroughly discussed with the subject. The subject must collect breastmilk sample and infant stool sample at baseline prior to the first dose (Day -2 to Day 1).
 
Updated Text:
 
The subject can use a manual or electric breast pump if she does not wish to manually express her breastmilk.
 
Timepoints for breastmilk and infant stool sample collection must be thoroughly discussed with the subject. The subject must collect breastmilk sample and infant stool sample (15ml) at baseline prior to the first dose (Day -2 to Day 1).
 
Removed text:
 
Teach the subject how to properly freeze her milk after expression each time until all samples are collected and shipped.
	
Allow more flexibility for methods subject can use to provide breastmilk samples
 
Breastmilk will be collected on site instead of home due to difficulty collecting and storing breastmilk properly and difficulty with transport of home collection to site in the required timeframe
 
Provided volume of stool sample required.

7.1.2 Procedure to be followed during Active Study Period (Day 1 to Day 29)	
Current Text:
 
...breastmilk sample (5ml-10ml)
 
...and to remind the subjects to collect and store breastmilk samples
 
Updated Text:
 
Ensure the subject collected baseline breastmilk sample (10ml) and infant stool sample between D-2 to D1.
 
Removed Text:
 
deleted "5ml"
 
deleted "and to remind the subjects to collect and store breastmilk samples."
	Subjects not required to collect breastmilk samples at home due to logistics as mentioned previously
7.1.3 Procedure to be followed during follow-up period (Day 30 to Day 365)	
Updated Text (added number 4)
 
4. Collect the most current infant vaccine record on Day 60 or any time after.
 
Removed Text (bullet 7):
 
For Day 120, determine if the subjects are still breastfeeding; if yes then remind the subjects to collect and store breastmilk samples
	
Required for inclusion criterium 8c assessment.
 
Breastmilk will not be collected at home due to difficulty collecting and storing breastmilk properly and difficulty with transport of home collection to site in the required timeframe

8.1.4 Pregnancy Testing	
Current Text:
 
If a pregnancy is reported, the Investigator should inform the Sponsor within 24 hours of learning of the pregnancy and should follow the procedures outlined in Section 9.1.7.
 
Updated Text:
 
If a pregnancy is reported, the Investigator should inform the Sponsor within 24 hours
	Correct section specified with link retained for 9.5.4 (page 48). Edited for accuracy.

	of learning of the pregnancy and should follow the procedures outlined in Section 9.5.4.	
8.2.1 Primary Immunogenicity Assessments:	
Current Text:
 
Breastmilk VPI specific (GI.1 and GII.4) IgA through the active period measured by Meso Scale Discovery (MSD) assay by dose level
 
Geometric mean concentration (GMC) at Day 1, Day 8, Day 15 and Day 29
 
Geometric mean fold rise (GMFR) from Day 1 to Day 8, from Day 1 to Day 15, and from Day 1 to Day 29
 
Current Text:
 
Breastmilk VPI specific (GI.1 and GII.4) IgA through the active period measured by Meso Scale Discovery (MSD) assay by dose level
 
Geometric mean concentration (GMC) at Day 1, Day 8 and Day 29
 
Geometric mean fold rise (GMFR) from Day 1 to Day 8 and from Day 1 to Day 29
	Align with Schedule of Activities and intended immunogenicity analysis
8.2.2 Immunogenicity Assessments:	
Current Text:
 
Immunogenicity Endpoints
 
Updated Text:
 
Secondary Immunogenicity Endpoints
 
Current Text:
 
Breastmilk VP1 specific (GI.1 and GII.4) IgA through 6 months after study drug dose measured by Meso Scale Discovery (MSD) by dose level
	
Added "Secondary" to Immunogenicity Assessments to categorize objectives more clearly and appropriately.
 
Align with Schedule of Activities and intended immunogenicity analysis

	
Geometric mean concentration (GMC) at Day 60, Day 120 , and Day 180
 
Geometric mean fold rise (GMFR) from Day 1 to Day 60, from Day 1 to Day 120, and from Day 1 to Day 180
 
Updated Text:
 
Breastmilk VP1 specific (GI.1 and GII.4) IgA through 6 months after study drug dose measured by Meso Scale Discovery (MSD) by dose level
 
Geometric mean concentration (GMC) at Day 60 and Day 180
 
Geometric mean fold rise (GMFR) from Day 1 to Day 60, and from Day 1 to Day 180
	
11.4.3 Analysis of Primary, Secondary, and Exploratory Immunogenicity and Endpoints	
Current Text:
 
Immunogenicity samples will be drawn for all subjects and their infants. Immunogenicity analyses will be based upon results from appropriately sized subsets of samples, according to the purpose.
 
Updated Text:
 
Immunogenicity samples will be drawn for all subjects. Immunogenicity analyses will be based upon results from appropriately sized subsets of samples, according to the purpose.
	Deleted "and their infants." Clarified we will not be collecting serum from infants
14.1 Early Safety Data Review AND/OR Committee	
Current Text:
 
Two or more subjects experience the same treatment-related unsolicited grade ≥ 3 AE between Day 1 and Day 29 (Active Period).
 
Updated Text:
	There is no numerical grade for unsolicited AEs.

	Two or more subjects experience the same treatment-related unsolicited grade “severe” AE between Day 1 and Day 29 (Active Period).	
Appendix 4: Contraceptive Guidance and Collection of Pregnancy Information	
Updated Text (added):
 
Contraceptive Guidance
 
Contraceptive use by women should be consistent with local regulations regarding the use of contraceptive methods for those participating in clinical studies. Subjects must be willing to use a highly effective form of contraception for 30 days prior to vaccination and until 60 days after the vaccination. Acceptable forms are oral, implantable, intrauterine, transdermal, intravaginal, injectable, double barrier or abstinence (subjects using diaphragms must also use condom). A reliable form of contraception must be approved by the Investigator.
 
While abstinence is allowed, periodic abstinence (e.g., calendar, ovulation, symptothermal, post-ovulation methods) and withdrawal are not acceptable methods of contraception.
 
A negative pregnancy test will be required for all female subjects prior to study drug administration, as outlined in the SoA (Table 1).
	
Added to emphasize which contraceptive method is allowed and to clarify that periodic abstinence is not allowed
 
Contraceptive Guidance. Moved to correct section

**Document History - Updates made from SAP (Version 1.0)**

• Changes in SAP text:

○ Not Applicable

• Reason for this update:

○ Not Applicable

• Changes in Mock shell:

○ Not Applicable

• Reason for this update:

○ Not Applicable

**List of Abbreviations**

Abbreviation	Description
AE	Adverse event
AESI	Adverse event of special interest
AEFI	Adverse events following immunization
ASC	Antibody secreting cells
ATC	Anatomical Therapeutic Class
AU	Arbitrary Unit
BMI	Body mass index
BT50	Blocking Titer 50
CI	Confidence Intervals
eCRF	Electronic case report form
CS	Clinically Significant
CSR	Clinical Study Report
DBP	Diastolic blood pressure
EDC	Electronic Data Capture
EOS	End of Study
ET	Early Termination
GCP	Good Clinical Practice
GI.1	Norovirus genogroup I.1
GI.4	Norovirus genogroup II.4
GRAS	Generally recognized as safe
HBsAg	Hepatitis B surface antigen
HBGA	Histo-blood group antigen
HCV	Hepatitis C virus
HIV	Human immunodeficiency virus
ICF	Informed Consent Form
IP	Investigational Product
ITT	Intent to treat
IgA	Immunoglobulin A
IgG	Immunoglobulin G
IQR	Interquartile Range
IU	Infectious Units
LLD	Lower Limit of Detection
LLOQ	Lower Limit of Quantification
MedDRA	Medical Dictionary for Regulatory Activities
MSD	Meso Scale Discovery
N/A	Not Applicable
NCS	Not Clinically Significant
NK	Not Known
NOCI	New Onset of Chronic Illness
NoV	Norovirus
PD	Pharmacodynamic
PI	Principal investigator
PK	Pharmacokinetic
PT	Preferred Term
SAE	Serious adverse event
SAP	Statistical analysis plan
SBP	Systolic blood pressure
SD	Standard Deviation
SMC	Safety Monitoring Committee

Abbreviation	Description
S.I.	International System of Units
SoA	Schedule of Activities
SOC	System Organ Class
SOP	Standard Operating Procedure
TEAE	Treatment-emergent adverse event
VP1	Viral Protein 1, major capsid protein of norovirus
WHO	World Health Organization
WHO-DD	World Health Organization Drug Dictionary

---

## 1. INTRODUCTION

The following Statistical Analysis Plan (SAP) provides the outline for the statistical analysis of the data collected from the VXA-NVV-108 study (protocol version 2.0 dated 25 July 2023) and its associated electronic case report forms (eCRF) Version 3.0, dated 06 December 2023.

The planned analyses identified in this SAP may be included in clinical study reports (CSRs), regulatory submissions, or future manuscripts. Also, post hoc exploratory analyses not necessarily identified in this SAP may be performed to further examine study data. Any post hoc, or unplanned, exploratory analyses performed will be clearly identified as such in the final CSR.

The preparation of this SAP has been based on the International Council for Harmonization (ICH) E9 and Good Clinical Practice (GCP) E6 guidelines.

## 2. PROJECT OVERVIEW

[figure not shown]
### 2.1 Study Design

This is a multi-center, double-blind, randomized, placebo-controlled, single dose, dose ranging study in healthy, breastfeeding, female volunteers ( $\geq 18$  years). The study will randomize 76 subjects and their breastfed infants aged  $>30$  days to 11 months of age into three arms.

After reviewing and signing an informed consent, the subjects will undergo screening assessments to determine study eligibility up to a 45-day Screening Period.

On Day 1 of the randomized portion, subjects will be randomized in a 30:30:16 ratio to one of the three treatment arms to receive active vaccine at medium dose or high dose or placebo, as follows (Figure 1):

**Figure 1: Study Design**

After vaccination on Day 1, the study will include an Active Study Period that runs through 4 weeks after administration (Day 29), and a Follow-up Period of one-year post-dose for safety and duration of immune response. Study assessments will be conducted as shown in the SoA (Table 1). In addition, subjects will be contacted by phone between site visits to monitor for safety as specified in the SoA (Table 1).

A subject is considered to have completed the study if she completes the study active period at Day 29 (End of Study Active Period). Following completion of the Day 29 visit by all subjects the database will be cleaned and locked and the study unblinded, except the medical monitoring and pharmacovigilance team including anyone at the Sponsor, CRO and sites(s). The Topline Clinical Study Report (CSR) will be written based on the Day 29 clean datasets.

A subject is considered to have completed the Follow-up Period if she remains in the study through Day 365 (Month 12). Following completion of the Day 365 tele-health appointment for all subjects, the safety database will be cleaned and locked, and data collected during the Follow-up Period will be included in a CSR addendum.

All subjects will be monitored for Solicited Symptoms of Reactogenicity (GI and systemic) for 1 week following the study drug dose (until Day 8 (+2 days) scheduled site visit) and unsolicited AEs for 28 days post study drug dose (until Day 29 scheduled site visit) during the active period. Subjects will then enter the Follow-up period after Day 29 and will be monitored for specified unsolicited adverse events (SAEs, AESIs, and NOCIs) through Day 365 (Month 12) for safety and durability of immune response. Subjects will provide samples (nasal, saliva, serum, breast milk, and infant stool for evaluation of immunogenicity as specified in the Schedule of Activities (SoA) (Table 1).

**Table 1: Schedule of Activities**

	Screening	Active Study Period				Follow-up Period					
Study Day	Day -45 to Day -1	Day 1	Day 8 (ET) f	Day 15	Day 29 (ET) f	Month 2 Day 60 g	Month 4 Day 120	Month 6 Day 180	Month 8 Day 240	Month 10 Day 300	Month 12 Day 365
Telephone call visit			+ 2	±2	±2	±7	±7	±7	±7	±7	±7
Visit Window (days)			+ 2	±2	±2	±7	±7	±7	±7	±7	±7
Informed consent	X										
Inclusion/Exclusion	X	X									
Demographics	X										
Medical history a	X	X									
Serology a	X										
Urine drug screen	X										
Alcohol test	X	X									
Pregnancy Test b	X	X									
Physical examination	X	X c	X c		X c						
Vital Signs d	X	X	X		X						
Study Drug Administration		X									
Distribute Solicited Symptom Diary		X									
Review Solicited Symptom Diary e			X f								
Review prior & concomitant medication	X	X	X	X	X						
Query for AEs, SAEs, AESIs and NOCIs		X	X	X	X	X g	X g	X g	X g	X g	X g

Study Day	Screening	Active Study Period				Follow-up Period					
	Day -45 to Day -1	Day 1	Day 8 (ET) f	Day 15	Day 29 (ET) f	Month 2 Day 60 g	Month 4 Day 120	Month 6 Day 180	Month 8 Day 240	Month 10 Day 300	Month 12 Day 365
Telephone call visit				☎ e			☎ e		☎ e	☎ e	☎ e
Visit Window (days)			+ 2	±2	±2	±7	±7	±7	±7	±7	±7
Sample Collection for Immunogenicity Assessments											
Serum sample - BT50, VP1 specific IgA and IgG		X	X		X			X			
Nasal Swab (SAM TM Device) - VP1 specific IgA		X	X		X	X		X			
Saliva Sample - VP1 specific IgA		X	X		X	X		X			
Breastmilk - VP1 specific IgA, Enterocyte culture neutralizing antibodies, and BT50 h		X	X		X	X		X			
Infant Stool - VP1 specific IgA		X			X	X					

## Notes:

Tele-health appointment (by phone)

a F- human immunodeficiency virus (HIV), Hepatitis B surface antigen (HBsAg) or Hepatitis C virus (HCV)

b Serum pregnancy tests will be done at screening. Point-of-Care urine pregnancy test will be performed before dosing on Day 1 and women found positive with urine pregnancy test will not be enrolled during this study.

c Targeted exam: at a minimum, assessments of the skin, respiratory system, cardiovascular system, and GI (abdomen, liver, and spleen) will be included.

d Blood pressure, heart rate, and respiratory rate will be measured after the subject has been resting in a sitting position for 5 minutes.

e At the discretion of PI and/or per subject request to evaluate any of the expected reactogenicity symptoms or any unexpected symptoms of concern, a contact must occur as soon as possible between the subject and the Investigator, or a medically qualified member of the study site staff, to assess if an unscheduled visit is required.

f Early termination assessments. Review of solicited symptoms should be included if the subject drops out before Day 8. Day 29 procedures should be performed if the subject drops out before Day 29 on the day of early termination.

g TEAEs will only be collected during the Active Study period (from time of first dose through 4 weeks post dose). Only SAEs, AESIs and NOCIs will be collected during the Follow-up Period.

h Breastmilk VP1 specific IgA will be tested at the indicated intervals in the table. Breastmilk enterocyte culture neutralizing antibodies and BT50 will be tested at various time points if feasible.

\* Also collect the infant's medical record at screening and day 1 and the infant's updated vaccine record at D60 or later

## 2.2 Objectives

### 2.2.1 Primary objective(s)

- **Safety**
  - To determine the safety and tolerability of oral bivalent dosing regimen of GI.1 and GII.4 norovirus vaccine administration in healthy lactating female participants.
- **Immunogenicity**
  - To determine the short-term immunogenicity of oral bivalent GI.1/GII.4 norovirus vaccine administration in healthy lactating female participants and most critically, the association with vaccine specific antibody responses in breast milk.

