This study will investigate the safety, tolerability, and immunogenicity of two distinct monovalent norovirus oral vaccine products given together as a single bivalent dose. Both vaccine drug products (DP) will be supplied in the form of small white enteric-coated tablets containing VXA-G1.1-NN or VXA-G2.4-NS.

VXA-G1.1-NN and VXA-G2.4-NS are E1/E3-deleted, replication-incompetent, serotype 5 adenovirus vaccine vectors designed for use as vaccines for the prevention of NoV infection. These non-replicating vectors encode for a full-length VP1 gene of either Norwalk virus (VXA-G1.1-NN vaccine) or Sydney virus (VXA-G2.4-NS vaccine). In addition to the transgene cassette, the rAd5 vector also contains a dsRNA hairpin following a second hCMVie promoter, thereby expressing both vaccine antigen and adjuvant in the same cell. These rAd5 vectors are designed to deliver both NoV VP1 antigen and adjuvant to the same target cells in the intestinal ileum.

A matching number of placebo tablets will be dispensed to maintain the study blinding.

Objectives and Endpoints:

Primary Objective	Primary Endpoints

To evaluate the safety and tolerability of oral bivalent GI.1/GII.4 norovirus vaccine administration in healthy lactating female participants.To assess the short-term immunogenicity of oral bivalent GI.1/GII.4 norovirus vaccine administration in healthy lactating female participants and its association	
Frequency, duration, and severity of solicited symptoms of reactogenicity (local and systemic) for 1 week following study drug dose.Frequency, duration, and severity of unsolicited treatment-emergent adverse events (TEAEs), serious AEs (SAEs), adverse events of special interest (AESIs), and new onset of chronic illness (NOCIs) through the active period (4 weeks post dose).Serum VP1 specific (GI.1 and GII.4) IgA on Day 1 (baseline), Day 8, and Day 29 (4 weeks post last dose).Breastmilk VPI specific (GI.1 and GII.4) IgA on Day 1 (baseline), Day 8, , and Day 29 (4 weeks post last dose).

with the immunogenicity response in breastmilk.	
Secondary Objective	Secondary Endpoints

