
 To assess the long-term safety of bivalent GI.1/GII.4 norovirus vaccine through 12 months after the last vaccination. To assess the immunogenicity of oral bivalent GI.1/GII.4 norovirus vaccine administration in healthy lactating female participants and its association with the immunogenicity response in breastmilk. 	
 Frequency, duration, and severity of all SAEs, AESIs, and NOCIs through 12 months after study drug dose Serum VP1 specific (GI.1 and GII.4) IgA on Day 180 after study drug dose Breastmilk VP1 specific (GI.1 and GII.4) IgA on Day 60, , and Day 180 after study drug dose Serum VP1 specific (GI.1 and GII.4) IgG on Day 1 (baseline), Day 8, Day 29, and Day 180 after study drug dose Serum BT50 (GI.1 and GII.4) on D1 (baseline), on Day 8, Day 29, and Day 180 after study drug dose
Exploratory Objective	Exploratory Endpoints

 To assess additional immunogenicity parameters of bivalent GI.1/GII.4 norovirus vaccine including immunogenicity response in breastfed infants. To assess clinical effects in subjects presenting with acute gastroenteritis symptoms during the study period 	
 Nasal and saliva VP1 specific (GI.1 and GII.4) IgA from lactating mother on D1 (baseline), on Day 8, Day 29, Day 60, and Day 180 Infant stool VP1 specific (GI.1 and GII.4) IgA on Day 1 (baseline), Day 29, and Day 60 Breastmilk BT50 (GI.1 and GII.4) at various, critical timepoints if feasible, and with samples that have high probability of significant responses Breastmilk Enterocyte culture neutralizing antibodies (GI.1 and GII.4) at various timepoints, if feasible, and with samples that have a high probability of significant responses. Occurrence of norovirus acute gastroenteritis

Study Population:

76 healthy adult lactating female participants aged 18 years or greater and their breastfed infants aged >30 days to 11 months of age

Planned Number of Subjects:

A total of 76 healthy lactating female participants aged ≥ 18 years and their breastfed infants aged >30 days to 11 months of age will be enrolled and randomized during this trial.

Eligibility Criteria:Inclusion Criteria:

To be eligible for this study, participants must meet all the following:

1. Lactating females aged ≥ 18 years at the time of enrolment and their breastfed infants aged >30 days to 11 months of age at the time of the participants' study drug administration.

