3. TRIAL OBJECTIVE AND END POINTS

3.1. Objectives

3.1.1. Primary Objectives

- **Safety**
 - To determine the safety and tolerability of oral bivalent dosing regimen of GI.1 and GII.4 norovirus vaccine administration in healthy lactating female participants.
- **Immunogenicity**
 - To determine the short-term immunogenicity of oral bivalent GI.1/GII.4 norovirus vaccine administration in healthy lactating female participants and most critically, the association with vaccine specific antibody responses in breastmilk.

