### 2.2.2 Secondary objective(s)

- **Safety**
  - To determine the long-term safety of bivalent GI.1/GII.4 norovirus vaccine through 12 months after the last vaccination.
- **Immunogenicity**
  - To assess the long-term immunogenicity of oral bivalent GI.1/GII.4 norovirus vaccine administration in healthy lactating female participants and most critically, the association with vaccine specific antibody responses in breast milk.

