## 2.3 Endpoints

### 2.3.1 Primary endpoints

- **Safety:**
  - Frequency, duration, and severity of solicited symptoms of reactogenicity (local, systemic) for 1 week following each dose of study drug.
  - Frequency, duration, and severity of unsolicited treatment-emergent adverse events (TEAEs), serious AEs (SAEs), adverse events of special interest (AESIs), and new onset of chronic illness (NOCIs) through the active period (4 weeks post last dose).
- **Immunogenicity:**
  - Serum VP1 specific (GI.1 and GII.4) IgA through the active period measured by Meso Scale Discovery (MSD) assay by dose level
    - Geometric mean concentration (GMC) at Day 1, Day 8 and Day 29
    - Geometric mean fold rise (GMFR) from Day 1 to Day 8 and from Day 1 to Day 29
    - The number of subjects in each dose group that had a 2-fold, 3-fold and 4-fold GMC rise or greater in serum VP1 specific IgA (GI.1 and GII.4) between Day 1 and any other timepoint.
  - Breast Milk VPI specific (GI.1 and GII.4) IgA through the active period measured by Meso Scale Discovery (MSD) assay by dose level
    - Geometric mean concentration (GMC) at Day 1, Day 8, and Day 29
    - Geometric mean fold rise (GMFR) from Day 1 to Day 8, and from Day 1 to Day 29

- The number of subjects in each dose group that had a 2-fold, 3-fold and 4-fold GMC rise or greater in breast milk VP1 specific IgA (GI.1 and GII.4) between Day 1 and any other timepoint.

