### 3.3 Inferential Analyses

No formal hypothesis testing is planned.

Descriptive statistics will be used to summarize the safety and immunogenicity data.

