**Statistical Method:**

All immunogenicity data collected at scheduled and unscheduled visits will be included in the listings, but only results collected as scheduled visits will be included in the summary tables.

All results will be presented descriptively and summarized by treatment arms.

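### The objective called most critical, the association between the mother's response and the breast-milk response, has no planned analysis

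*SAP*

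**What the plan says.** Both documents give the association pride of place. Protocol v2.0 section 3.1.1 asks for short-term immunogenicity in the mothers and "most critically, the association with vaccine specific antibody responses in breastmilk"; SAP 2.2.1 likewise asks for "most critically, the association with vaccine specific antibody responses in breast milk". The secondary objective repeats it in Protocol 3.1.2 and, for the longer term, in SAP 2.2.2: "To assess the long-term immunogenicity of oral bivalent GI.1/GII.4 norovirus vaccine administration in healthy lactating female participants and most critically, the association".

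The protocol synopsis is clearer about what is associated with what. Its primary objective speaks of immunogenicity of "vaccine administration in healthy lactating female participants and its association", continuing with the response in breast milk, and its secondary objective ends "and its association with the immunogenicity response in breastmilk".

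The endpoints and methods then treat each sample type alone. SAP 2.3.1 opens its primary list with "Serum VP1 specific (GI.1 and GII.4) IgA through the active period measured by Meso Scale Discovery (MSD) assay by dose level" and has a parallel item for milk. Each is reported as geometric means, geometric mean fold rises and counts of women with at least a 2-, 3- or 4-fold rise. SAP 3.3 says "Descriptive statistics will be used to summarize the safety and immunogenicity data", and the statistical method in section 14 adds "All results will be presented descriptively and summarized by treatment arms". Protocol 11.4.3 also plans descriptive summaries only.

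**The concern.** Mean serum IgA and mean milk IgA can both rise after vaccination without the women who respond more in serum being those who respond more in milk. Separate summaries by arm cannot show whether they are. The part of the primary objective that the sponsor ranks highest would then be left unanswered or filled in later.

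SAP section 1 allows unplanned work only if it is labelled post hoc. By then the study is unblinded, because unblinding follows the Day 29 lock (SAP 2.1 and 16). Visit, scale, choice of arms and handling of values below the quantification limit would all be chosen with the data in view.

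**Working it through.** **Search for any serum-to-milk link**

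| Place | Content | Serum related to milk within a woman? |
|---|---|---|
| SAP 2.3.1, 2.3.2 | Geometric means, fold rises, fold-rise counts, per sample type | No |
| SAP 14 and Protocol 11.4.3 | Descriptive, by arm | No |
| SAP 18, Tables 14.2.1.x to 14.2.4.x | One sample type per table; 2 × (3 + 4 + 3 + 1) = 22 tables over two analysis sets | No |
| SAP 19, Listings 16.2.6.1 to 16.2.6.8 | Serum and milk in separate listings | No |
| SAP 20, Figures 14.2.1.1 to 14.2.8.1 | Bar plots, one sample type each | No |
| SAP 15 | Adds fold-rise counts, reduces BT50 visits | Association not mentioned |

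No correlation, regression, scatter plot or responder cross-tabulation appears.

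**Are paired data scheduled?** Yes. SAP Table 1 has serum and milk at Days 1, 8, 29 and 180. Day 60 has milk but no serum. Serum is reported in AU/mL and milk in RLU per µg of total IgA, so within-woman fold rise is the natural common scale.

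**What precision is possible?** The planned arms are 30 medium dose, 30 high dose and 16 placebo (30 + 30 + 16 = 76). The plan has no power calculation and no correlation to reproduce, so r is assumed over a range and all pairs are taken as complete. The Fisher z interval is tanh(atanh(r) ± 1.96/√(n − 3)).

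For r = 0.5, atanh(0.5) = 0.549. The half-width is 1.96/√57 = 0.260 for n = 60 and 1.96/√27 = 0.377 for n = 30.

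| Assumed r | Both vaccine arms, n = 60 | One arm, n = 30 |
|---|---|---|
| 0.3 | 0.05 to 0.51 | −0.07 to 0.60 |
| 0.5 | 0.28 to 0.67 | 0.17 to 0.73 |
| 0.7 | 0.54 to 0.81 | 0.45 to 0.85 |

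This formula is for an unadjusted Pearson correlation. For a Spearman correlation adjusted for arm (one covariate), the Bonett–Wright standard error is √[(1 + r²/2)/(n − 3 − 1)]. At r = 0.5 and n = 60 this is √(1.125/56) = 0.142, giving about 0.27 to 0.68. If 20% of pairs were missing (an assumption; n = 48), it is √(1.125/44) = 0.160, giving about 0.23 to 0.70.

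**Why placebo should stay separate.** Suppose there is no correlation within arms and vaccination shifts both serum and milk by d standard deviations. Mixing 60 vaccinated and 16 placebo women gives r = c·d²/(1 + c·d²), with c = 60 × 16/76² = 0.166. That is 0.14 at d = 1, 0.27 at d = 1.5 and 0.40 at d = 2, from the arm difference alone.

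**The case against.** The strongest reply is that the phrase in Protocol 3.1.1 and SAP 2.2.1 has no stated first term. It could mean the association of vaccination with milk antibody, and Protocol 2.3 does describe the study as evaluating the vaccine's immunogenicity effect in milk. On that reading the by-arm milk summaries address the objective descriptively. The ambiguity is real, and rewording the objective would be a legitimate answer. The synopsis, however, ties the association to the mother's immunogenicity. Even on the looser reading, section 14 specifies no vaccine-to-placebo ratio or difference for milk IgA.

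A second reply is that the study is openly descriptive, with no hypothesis tests, and that the SAP simply follows the protocol's endpoints. The gap does start in the protocol, whose endpoints define no association measure. But a correlation with a confidence interval is descriptive, and section 14 already plans intervals for geometric means. The planned listings would let a reader match individual values by hand, but they give no estimate.

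Three stronger readings are tempting and not supported:
- **That the trial is already known to give usable precision.** The documents contain no correlation, and SAP 14 says analyses may use subsets of samples.
- **That any later correlation would be spurious through pooling with placebo.** No document proposes such pooling. It could inflate a correlation if arm is ignored, which is a reason to state the rule in advance.
- **That Day 180 can be handled just like Day 29.** Protocol 7.1.3 seeks follow-up milk only from women still breastfeeding, and inclusion criterion 7 requires a plan for only one month.

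**Conclusion.** The point holds. None of the planned immunogenicity tables, listings or figures relates a woman's serum response to her milk response, so the plan as written cannot report on the part of its primary objective ranked most critical. The secondary objective has the same gap. Nothing records a decision to drop the analysis, so it reads as an omission.

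The conclusion rests on the synopsis wording as the sponsor's meaning. The precision figures are illustrations under assumed correlations and complete pairs. They suggest a moderate or strong association could be estimated reasonably well with both vaccine arms combined, and only roughly in one arm. This is a gap in pre-specification; it does not call for a hypothesis test or a larger sample.

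**What to change.** Before the Day 29 lock and unblinding, add to SAP section 14, for each strain:

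- the Spearman correlation of serum IgA fold rise with milk IgA fold rise in women with both samples, in the two vaccine arms combined with adjustment for dose arm, and also by arm, with a 95% CI using a Spearman-appropriate standard error;
- a scatter plot by arm;
- Day 8 and Day 29 for the primary objective and Day 180 for the secondary, with the number of pairs at each;
- values below the quantification limit handled by the SAP 3.5 rule;
- placebo shown separately;
- a statement that Day 180 pairs come only from women still breastfeeding and may be fewer and selected.

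A regression slope of milk on serum response is optional. If the sponsor intended only the vaccine's effect on milk antibody, reword the objective instead and record this in SAP section 15.

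The cost is one extra table and figure per strain, with no new sampling. The drawback is wide intervals within a single arm, which the report should state.
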